1 INTRODUCTION: BACKGROUND AND SCIENTIFIC RATIONALE

1.1 Background Information

Dupuytren's Disease (DD) is a benign fibroproliferative condition, which although generally painless, it gradually causes flexion contractures to the digits and causes functional problems to those who have it. Although multiple etiologies have been implicated in this condition, it is thought to be mostly transmitted through autosomal dominant gene with variable penetrance affecting primarily patients with Northern European ancestry[1]. A recent systematic review and meta-analysis has shown that prevalence of DD in Western countries varies from 0.6% to 31.6% and increases steadily with increasing age [2]. Another recent review of prevalence and incidence in the United States found that prevalence ranged from 0.5% to 11% consistent with the 4-6% prevalence rates found in previous studies of general populations and concluded that there are a number of unmet medical needs particularly for better understanding, recognition and treatment of DD [3]. Many surgical approaches have been introduced over the years to deal with DD including percutaneous needle aponeurotomy, open fasciotomy, and commonly limited open palmar fasciectomy[4,5]. Non-surgical management options such as injections with steroids or verapamil have been previously proven ineffective and rejected clinically[6]. Limited palmar fasciectomy (LPF) has been the most common and widely accepted treatment for this condition. In the last 6 years however, collagenase injection (CI) has been making inroads as a legitimate treatment for DD. A multicentre double-blind RCT in 2009 (CORD I study) comparing collagenase to placebo has demonstrated its clinical safety and efficacy[7]. A second multicentre double-blind study also comparing collagenase to placebo (CORD II study) in 2010 confirmed that collagenase is effective and well tolerated in DD[8]. A number of adverse effects have been associated with collagenase injections but these are mostly well tolerated by patients. The most severe complication is tendon rupture which is rare, with an overall incidence at around 0.5% in previous randomized, double-blind, placebo-controlled studies[7-9]. Technical tips have been provided by a number of authors to avoid this complication[6-8]. A more recent study (CORDLESS study) in 2013 evaluated the long term efficacy and safety of collagenase treated patients in 5 previous clinical studies (which included both CORD RCTs in addition to 3 open-label trials) over a 3 year period and found that the recurrence rate was comparable to the surgical approaches to DD. Furthermore, they found no long term adverse effects[10]. This study has subsequently published 5 year follow-up results for the same cohort and has concluded that collagenase is an effective and safe treatment for DD with comparable recurrence rates after surgical treatments[11].

The two previous RCTs (CORD I and CORD II) have greatly influenced the adoption of collagenase, which now stands as a legitimate contender to palmar fasciectomy for DD.

The main methodological weakness of the CORD I and CORD II trials is that the comparative intervention was placebo. Many trial methodologists would be concerned with using a placebo when existing surgical techniques exist such as the commonly performed palmar fasciectomy. We believe that presently, we are uncertain if collagenase, a non-surgical treatment is superior to palmar fasciectomy, a surgical treatment. An RCT is warranted for a head-to-head comparison. Zhou et al. directly compared CI to LPF in a propensity score matched study and found that CI was not significantly different from LPF in reducing metacarpophalangeal joint contractures. CI was also inferior to LPF in correcting proximal interphalangeal joint contractures. On the positive side, CI provided a more rapid recovery of hand function than LPF and was associated with fewer serious adverse events [12]. However, their study evaluated only short-term clinical results at 12 weeks after surgery and included a minimal number of recurrent cases in their sample. They also acknowledge the limitation of propensity matching in terms of confounding and that a well-designed randomized trial would help eliminate some confounding factors. Their overall conclusion stated that long-term effectiveness trials are still needed in head-to-head comparison studies. Based on the available evidence we believe that there presently exists a state of equipoise, which is a precondition for an RCT comparing the effectiveness of these two approaches.

A previous cost-effectiveness study by Baltzer and Binhammer found that the collagenase injection was cost-effective from the societal perspective[5]. Our appraisal of the study however, identified some methodological weaknesses. That study used a decision analysis model which was not an ideal study design as it relies on secondary data. A trial-based cost-effectiveness analysis would be greatly strengthened by its access to individual patient level data collected directly from the trial cohort. In addition, Brazzelli et al has published a systematic review and economic evaluation in October 2015 [13] concluding that there is no evidence that CI is clinically better or worse than surgical treatments and that LPF appears to be the most cost-effective choice for moderate to severe contractures. However, the results of their cost-utility analysis were based on an indirect comparison of clinical effectiveness. The Markov model they used for the CUA was fraught with considerable uncertainty about the appropriateness of many assumptions and parameters used in the model. They conclude that a RCT is required to confirm or refute these findings.

1.2 Rationale

No study to-date has compared both the clinical effectiveness and cost-effectiveness of collagenase injection versus limited palmar fasciectomy with patient derived data in a prospective RCT study. Therefore, we do not know for certain if collagenase is, indeed, a superior treatment for DD as previous studies imply. Furthermore, the collagenase

injections are costly and therefore, we need to know if this novel medical intervention is cost-effective from the patient, Ministry of Health (MOH), and societal perspectives.

2 STUDY OBJECTIVES

2.1 Primary Objective

The primary objective of this study is to compare the clinical effectiveness of collagenase injections (CI) versus limited palmar fasciectomy (LPF) as measured by the 12 month post-randomization Michigan Hand Questionnaire (MHQ) after adjusting for the pre-randomization MHQ score.

2.2 Secondary Objectives

Secondary objectives include the cost-effectiveness of CI versus LPF from the consumer (patient), payer (Ministry of Health) and societal perspectives and additional measures of clinical effectiveness.

3 STUDY DESIGN

3.1 General Design

This trial is a prospective, randomized, multicentre, parallel, pragmatic clinical trial to investigate the clinical effectiveness and cost-effectiveness of collagenase injection (CI) versus limited palmar fasciectomy (LPF) in the treatment of Dupuytren's disease.

3.2 Primary Outcome Measure

The primary outcome is Health-Related Quality of Life (HRQL) measured with the Michigan Hand Outcomes Questionnaire (MHQ), a hand-specific outcomes instrument [14], at one year post-treatment.

3.3 Secondary Outcome Measures

Secondary outcomes include:

- (a) HRQL measured with the Health Utility Index Mark 3 (HUI3), a generic multi-attribute health-status classification instrument [15].
- (b) HRQL measured with the Unité Rhumatologique des Affections de la Main (URAM), a disease-specific HRQL measure developed for Dupuytren's contracture [16].
- (c) HRQL measured with the Southampton Dupuytren's Scoring Scheme (SDSS), a disease-specific scoring system developed for Dupuytren's contracture [17].
- (d) Quality Adjusted Life Years (QALY) measured with the HUI3. QALY is an important component of Cost-Utility Analysis (CUA), a variant of Cost-Effectiveness Analysis

(CEA); therefore, we will be able to calculate incremental cost per QALY gained between the two treatments. Utility scores of HRQL derived from responses to the HUI3 questionnaire have the required measurement properties for calculating QALYs[18].

- (e) Self-reported healthcare utilization (e.g. visits to hand surgeons, family physician, parking costs, etc.) and productivity loss (e.g. time lost from work and leisure activities by patient and caregiver).
- (f) Range of motion (ROM) of hand joints measured with goniometry
- (g) Recurrence rates defined as an increase in joint contracture in any treated joint of at least 20 degrees at one year post-treatment.
- (h) Necessary Dupuytren's Disease treatments applied to the previously affected digit(s) (the digit(s) treated in the EXTEND trial) up to 4 years following their original (EXTEND trial) treatment.

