After the injections are completed, the patient's treated hand will be wrapped with a soft, bulky gauze dressing and kept elevated for the remainder of the day. The patient will return to the surgeon's office/clinic 1-7 days post-injection to assess if the contracture has resolved. If a contracture remains, a passive finger extension procedure, with or without local anesthesia as determined by the surgeon, will be undertaken in an attempt to disrupt the cord. If residual contracture remains the patient will return for a 30-day follow-up when the cord may be reinjected and the finger extension procedure repeated.

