5.4 Procedures for Training of Clinicians on the Interventions

As CI is the “novel” intervention in this RCT, we need to consider the learning curve. Participating surgeons will be expected to review the detailed description of the technique, by viewing the provided learning video (http://www.xiaflexrems.com/video/dupuytren/Xiaflex_REMS.html) and have performed at least 10 CI injections with successful correction of the extension deficit (less than 5°) without serious complication before they begin the enrollment in the study.

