8 STATISTICAL CONSIDERATIONS

8.1 General

Analysis of baseline characteristics will be performed using descriptive statistics reported by group as mean (standard deviation [SD]) or median (first quartile, third

quartile) for continuous variables and count (percent) for categorical variables. All analyses of primary and secondary outcomes will follow the intention-to-treat principles. We will use multiple imputation to handle missing data [25]. The results for comparisons between groups will be presented as mean difference (for continuous outcomes) and relative risk (for binary outcomes), corresponding 95% confidence intervals and associated p-values. P-values will be reported to four decimal places with p-values less than 0.001 reported as $p < 0.001$. All analyses will be performed using SAS software version 9.4 (Cary, NC, USA).

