8.3 Clinical Effectiveness Analysis

The clinical effectiveness of the collagenase will be assessed using the following HRQL instruments: MHQ, HUI3, URAM and SDSS (see section 6.4 for details). Objective measures of ROM will also be conducted and used to evaluate improvement and recurrence rates.

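### Recurrence outcome (g) does not require that the joint was first corrected, so its relative risk mixes correction with durability and can favour the arm that corrects less

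*Combined protocol and SAP*

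**What the plan says.** Section 3.3(g) defines the outcome as "Recurrence rates defined as an increase in joint contracture in any treated joint of at least 20 degrees at one year post-treatment". The wording fixes the size of the increase and the time of assessment. It sets no condition that the joint was straightened first, and no reference visit for the increase.

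Section 8.3 adds only this: "Objective measures of ROM will also be conducted and used to evaluate improvement and recurrence rates". Section 6.3 and the Appendix schedule give the ROM visits (baseline, then 1, 3, 6 and 12 months) but no scoring rule. Under section 8.1, "All analyses of primary and secondary outcomes will follow the intention-to-treat principles", and binary outcomes are compared by "relative risk (for binary outcomes), corresponding 95% confidence intervals and associated p-values".

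The one correction threshold in the plan, in section 5.4, is a requirement on surgeons before they enrol: "at least 10 CI injections with successful correction of the extension deficit (less than 5°) without serious complication". It is not tied to any outcome.

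The plan foresees incomplete correction after injection. Section 5.1 says: "If residual contracture remains the patient will return for a 30-day follow-up when the cord may be reinjected". Section 1.1 cites a propensity-matched comparison in which "CI was also inferior to LPF in correcting proximal interphalangeal joint contractures", and from the same comparison reports that "CI was not significantly different from LPF in reducing metacarpophalangeal joint contractures".

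**The concern.** A joint that was never straightened and stays as it was shows no increase. Under (g) it scores the same as a joint that was straightened and stayed straight for a year. Both sit in the denominator as free of recurrence. The first is a treatment failure and the second a success.

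If the arms differ in how often they correct the joint, the recurrence comparison carries that difference with it. The cited evidence gives a reason to expect a difference at PIP joints, and PIP is one of the two randomization strata (section 4.5.1). Comparative recurrence is part of the case for collagenase in section 1.1, so a recurrence relative risk from this trial is likely to be read as evidence on durability. As defined, it cannot separate durability from initial correction.

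**Working it through.** **Plan's own figures.** The plan gives none for recurrence. Its only sample-size figure is for the MHQ. With a difference of 8.7, SD 15.5, two-sided 5% and 80% power, the t-based size is 50.8, so 51 per group (102). Then 51/0.8 = 63.75, so 64 per group (128). Both match section 8.2. The 51 is used below for precision.

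**Notation, one joint per patient.**
- c = proportion corrected.
- r = risk of a 20-degree increase in a corrected joint.
- u = the same risk in an uncorrected joint.
- Increase measured from a post-treatment visit.

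Recorded recurrence under (g) = c·r + (1 − c)·u. Failure (not corrected, or recurred) = (1 − c) + c·r.

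**Inputs.** The documents give no values for c, r or u. Assumed: c = 0.70 (CI) and 0.90 (LPF); r = 0.20 in both arms, so durability after correction is identical by construction.

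**Step 1. Vary u.**

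| u | CI | LPF | RR under (g) |
|---|---|---|---|
| 0 | 0.140 | 0.180 | 0.78 |
| 0.05 | 0.155 | 0.185 | 0.84 |
| 0.10 | 0.170 | 0.190 | 0.89 |
| 0.20 | 0.200 | 0.200 | 1.00 |
| 0.30 | 0.230 | 0.210 | 1.10 |

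Example, u = 0.10: CI 0.14 + 0.30 × 0.10 = 0.17; LPF 0.18 + 0.10 × 0.10 = 0.19. The ratio departs from 1 only because correction differs. It favours CI when u < r and reverses when u > r.

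**Step 2. Failure on the same inputs.** CI 0.30 + 0.14 = 0.44; LPF 0.10 + 0.18 = 0.28; RR 1.57. This does not depend on u.

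**Step 3. Vary the correction gap (u = 0).** With LPF held at 90%, CI correction from 60% to 90% moves the RR under (g) from 0.12/0.18 = 0.67 to 1.00. The failure RR moves from 0.52/0.28 = 1.86 to 1.00. With equal correction there is no distortion.

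**Step 4. Reference visit.** If the increase is measured from the pre-treatment value, a corrected joint must lose all its correction and a further 20 degrees, while an uncorrected joint needs only about 20. An illustrative simulation assumed a baseline contracture of mean 45, SD 15 degrees; corrected joints at 0; failed joints keeping 80% of their contracture; and the same 12-month change (mean 8, SD 15) in every joint. With 60% (CI) and 80% (LPF) corrected, recorded recurrence was 3.5% and 1.8%, RR about 1.9, against the arm that corrects less. A post-treatment reference in the same simulation gave 1.00, because u equals r there.

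**Step 5. Precision at 51 per group.** SE of log RR = √(1/e₁ − 1/51 + 1/e₂ − 1/51), where e is expected events.
- Recurrence, u = 0: e = 7.14 and 9.18, SE 0.458, 95% CI for 0.78 about 0.32 to 1.91.
- Failure: e = 22.44 and 14.28, SE 0.275, 95% CI for 1.57 about 0.92 to 2.69.

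**The case against.** **The direction is not fixed.** A reader might infer that every failed correction is scored as no recurrence and that the relative risk must therefore favour CI. The documents do not support that. An uncorrected joint that worsens by 20 degrees is counted, and section 1.1 describes a disease that progresses, so u = 0 is the extreme case. A tilt towards CI needs three things together: fewer joints corrected by CI, u below r, and a post-treatment reference. This objection stands in full. What remains is that the relative risk mixes two things and can mislead.

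**The evidence for unequal correction is limited.** It is one non-randomised comparison with 12-week results, no rates are quoted, and it found no significant difference at MCP joints. Section 5.1 makes residual contracture conditional and provides for further treatment of it. Nothing in section 5.2 says that LPF always corrects fully. This stands, and it confines the concern mainly to PIP joints.

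**The word recurrence already implies prior correction.** Perhaps, but that does not settle the analysis. If uncorrected joints cannot recur yet all randomized patients stay in the denominator, recorded risk is exactly c·r, the u = 0 row. If they are dropped, the comparison rests on a subset formed after randomization, contrary to the intention-to-treat statement in section 8.1.

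**Failed correction shows elsewhere.** ROM (f), improvement in section 8.3, further treatment (h) and the questionnaires can all register it. True, so the information is not lost to the trial. But none of these changes the recurrence relative risk that would be reported.

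**The effect is small in this trial.** About 7 against 9 patients could not credibly support a durability claim. This limits the harm, though the point estimate would still be published and could be pooled.

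**A composite can be dominated by non-correction.** In the worked CI arm, 30 of the 44 failure percentage points are non-correction. This stands, and is why both components must be shown.

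**Conclusion.** The concern holds in a limited form. Outcome (g) lacks a correction requirement and a reference visit, so its relative risk mixes initial correction with durability and can favour the arm that corrects less. On the assumed 70% and 90% correction with equal 20% recurrence after correction, it runs from 0.78 (u = 0) through 1.00 (u = 20%) to 1.10 (u = 30%), while failure on the same inputs gives 1.57 against CI. All of these rates are assumptions.

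A reader might also infer that the bias would persist whatever reference visit is chosen. It would not in that form: a pre-treatment reference can reverse the direction. Naming a post-treatment visit is necessary but not sufficient, since the 0.78 already assumes one.

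The point affects one secondary outcome, mainly at PIP joints. The MHQ primary outcome and the sample size of 128 are untouched. It should be corrected before analysis, but it does not threaten the trial's main conclusion.

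**What to change.** In sections 3.3(g) and 8.3:

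1. State that the increase is measured from a named post-treatment ROM visit. The 3-month visit is one candidate, as it falls after any 30-day reinjection.
2. Fix one correction cut-off for outcome scoring before analysis, and say which joint or joints it applies to when several are treated. The investigators should choose it. The 5 degrees in section 5.4 and the 20 degrees in section 4.1 were set for other purposes.
3. Report the proportion corrected in each arm.
4. Make the between-arm intention-to-treat comparison on patient-level failure at 12 months: not corrected, or an increase of at least 20 degrees after correction. Show the two components separately by arm.
5. Report recurrence among corrected joints beside this, labelled as conditional and descriptive.

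The cost is wording only. ROM is already scheduled at baseline and at 1, 3, 6 and 12 months, so no new visits or data are needed. The downsides are one more composite to define, in which non-correction may dominate, and a CI result that may look less favourable than recurrence alone.

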4 STUDY ENROLLMENT AND WITHDRAWAL

Following receipt of verbal and written information about the study, the patient must provide **signed and dated informed consent** before any study related activity is carried out. Patients will be recruited from the practices of plastic hand surgeons in Ontario. Patients will be eligible for entry into this study if they meet all of the inclusion criteria and have no exclusion criteria present.

4.1 Inclusion Criteria

1. 18 years of age or older
2. Dupuytren's contracture of the metacarpophalangeal (MCP) joint or of the proximal interphalangeal (PIP) joint with a fixed flexion contracture of 20° or greater in at least 1 finger (not the thumb)
3. Demonstrated inability to simultaneously place the affected finger and palm flat on a table
4. Able to understand and communicate in English

4.2 Exclusion Criteria

1. Previous treatment of the primary joint within 90 days of study inclusion
2. Patients undergoing any concomitant procedure on the same hand (e.g. carpal tunnel release, stenosing tenosynovitis release)
3. Persistent extension deficit from a previous surgery of the same digit
4. Any chronic muscular or neuromuscular disorder affecting wrist or hand
5. Patient generally unfit for surgery
6. Patient with specific treatment preference
7. Bleeding disorder or recent stroke
8. Allergy to collagenase
9. Collagenase treatment or treatment with any investigational drug within 30 days of study inclusion

10. Use of a tetracycline derivative within 14 days of first dose of study drug (because tetracycline derivatives may inhibit the collagenolytic activity of mammalian collagenase homologs [i.e., matrix metalloproteinases])
11. Pregnant or breast feeding patients
12. Patients who do not have insurance coverage for collagenase injections
13. Patients who are unable to provide informed consent or are unable to complete quality of life questionnaires due to mental capacity or neuro-psychological problems.

4.3 Patient Screening Log

A Patient Screening Log will be used in this study to document all patients who have provided written informed consent and have been screened, including those who cannot be randomized.

4.4 Strategies for Recruitment and Retention

For the successful conduct and timely completion of the study, it is important that the collaborating surgeons see a high volume of patients with DD. We chose the participating surgeons as we know these practicing surgeons and their willingness to participate in the study. These practices in various cities represent the diversity of the general population in Ontario.

The surgeons involved in our study each perform LPF on an average of 60 patients per year. It is assumed that 50% of potential patients will either be ineligible or not enrolled due to refusal of consent. It is therefore anticipated that 50% of eligible patients will be recruited.

Assuming that at least 10 surgeons screen a total of 600 patients and 50% of patients screened will be enrolled it is likely that approximately 300 patients can be recruited over a 12 month period. Using the estimated sample size of 128, it is estimated that all the patients could be recruited over approximately a 6-month year period. If the actual rate of enrollment is better than predicted, the duration of patient recruitment will be shortened accordingly. If the actual rate of enrollment is worse than predicted, additional surgeons will be invited to participate in this trial.

Every reasonable effort will be made to follow all participants for the entire duration of the trial. We will collect contact information for a family member, name & address of workplace/business, email address, and any social media account details to make it easier to locate the participant. Patients will be contacted via telephone the week before each follow-up appointment as a reminder. We will try to coordinate the study-related

follow up visit with the regular clinical visit to avoid extra trips to the clinic. If this is not possible, we will provide the participants with a gift card and/or parking vouchers. Compromises will be made for participants who are unable or unwilling to come for a follow-up such as completing questionnaires via mail or email.

For the research staff, quarterly meetings or teleconferences will be organized to discuss the recruitment & retention issues and their troubleshooting options. A standard operations manual will be developed at the beginning of the trial, and this will be updated and circulated at regular intervals as necessary. We will try to hire study coordinators who can commit to the duration of the study. In any case, the coordinators will be required to maintain a log of all the participants and note any scheduling issues.

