4.5 Treatment Assignment Procedures

4.5.1 *Randomization Procedures*

Eligible, consenting patients will be randomly allocated (1:1) to receive either CI or LPF using block randomization to ensure equal group sizes. Allocation will be determined in advance using a computer-based random number generator and stratified by primary joint type (MCP or PIP). We will use central randomization via a web-based system generated by the Biostatistics Unit at St Joseph's Healthcare—Hamilton. The randomization will be blocked within strata using randomly permuted blocks of various sizes. Approximately 2-3 months prior to their procedure, eligible, consenting patients will be randomized to one of the 2 treatments.

4.5.2 *Masking Procedures*

Blinding of patient and surgeon will not be possible. No or very minor scar is expected from collagenase injections. For palmar fasciectomy however, a noticeable scar is expected. As such, the patients will know which procedure they received. Outcome assessors will be hand occupational therapists or physiotherapists who will perform the goniometric measurements. Although they cannot be blinded for the same reason, they nevertheless work independent of the surgeon and therefore the risk of bias in the measurements will be mitigated. The statistician for the study however, can be blinded as he will be unaware of group allocation (Study A vs Study B).

As the palmar fasciectomy can be performed some weeks later there is a risk of cross-over but this can be avoided by obtaining the consent for palmar fasciectomy in the same clinic visit as the randomization.

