8.2 Sample Size Determination

The sample size will be based on the 12 month post-randomization MHQ score adjusted for baseline MHQ score. According to the paper by London, Stepan and Calfee [26] the MCID for the total MHQ score from an ROC analysis of patients from a population with multiple hand and forearm diagnoses is 8.7. The MCID for the total MHQ score falls between 8-13 points (depending on the method used to obtain an MCID) with a mean equal to 10.8. If we adopt an MCID of 8.7 it will be in the lower end of the range of estimates which will require a larger sample size than if the MCID were larger. For an estimate of the SD of the total MHQ score for patients with DD we obtain a value of 15.0 from the one week pre-operative assessment and 16.0 for the 12 month post-operative assessment based on the papers by Thoma et al [27,28]. The midpoint of these two estimates is 15.5.

If we use $\alpha=0.05$, $\beta = 0.80$, $MCID=8.7$ and $SD=15.5$ for the sample size calculation, assuming a correlation value of 0.0 between baseline and 12-month post-randomization MHQ scores, based on the method outlined in Borm et al[29] the required total sample is 102 patients, or 51 per group. If we account for a 20% loss to follow-up rate the required sample increases to 128 (64 per group). These calculations assume that the relationship between the baseline and 12 month post-randomization MHQ scores is linear and that the slopes of the best fit lines of the two groups are parallel.

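### The primary comparison adjusts for baseline MHQ but names neither joint type, the stratification factor, nor surgeon, so some precision is given up if outcomes differ by either

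*Combined protocol and SAP*

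**What the plan says.** - **Surgeons.** Section 3.1 describes a multicentre trial. Section 4.4 plans recruitment "Assuming that at least 10 surgeons screen a total of 600 patients" and allows more surgeons to be added if enrollment lags. It also says that these surgeons each perform LPF. Section 5.4 requires each to have at least 10 prior successful CI procedures, remarking that "we need to consider the learning curve". That the same surgeons deliver both treatments is a well-supported inference, not an explicit statement.
- **Technique.** Section 5.2 leaves LPF technique, setting and anaesthesia to the surgeon's routine.
- **Randomization.** Section 4.5.1 specifies central allocation in permuted blocks, "stratified by primary joint type (MCP or PIP"). Neither surgeon nor centre is a stratum.
- **Analysis.** Section 2.1 states the primary comparison as 12-month MHQ "after adjusting for the pre-randomization MHQ score", and Section 8.2 sizes the trial on that basis. Section 8.1 sets general rules, and Section 8.3 lists the instruments without giving a model. No joint-type, surgeon or centre term appears for any outcome.

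**The concern.** Two factors known for every patient are missing from the stated comparison.

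Joint type is the factor by which the trial randomizes. Blocking within joint type already balances the arms on it. If joint type predicts 12-month MHQ and is left out of the model, the reported standard error does not reflect that balance and is too large.

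Surgeon is not balanced by design. If patients of different surgeons have different average outcomes, that variation stays in the error term, and chance differences in each surgeon's CI:LPF split add noise to the treatment difference. At stake is precision in a trial planned at about 80% power. In addition, whether to adjust for surgeon is left undecided in a trial where patients, surgeons and assessors know the treatment.

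**Working it through.** **Inputs.** From Section 8.2: alpha 0.05 (two-sided assumed), power 0.80 (printed as beta), difference 8.7, SD 15.5, baseline correlation 0.0, 102 evaluable. From Section 4.4: 10 surgeons, taken as equal in expected size. Assumed, because the documents give none: surgeon ICC from 0 to 0.20, with a surgeon effect common to both arms.

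**1. The plan's own figure.** n per arm = 2(1.960 + 0.842)² × 15.5² / 8.7² = 49.8. The t-based version gives 50.8, so 51. With correlation 0.0 the ANCOVA factor (1 − r²) is 1. This agrees with "the required total sample is 102 patients, or 51 per group". For dropout, 102/0.8 = 127.5, so 128. At 51 per arm the SE is 15.5 × √(2/51) = 3.07, and normal-approximation power is 80.9%. The sample size reproduces.

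**2. Imbalance within surgeon.** With 128/10, about 13 randomized patients per surgeon, and treating allocations as independent, P(9:4 or worse) = 2(1 + 13 + 78 + 286 + 715)/2¹³ = 0.267. About 2 to 3 of 10 surgeons would be that unbalanced.

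**3. What that imbalance does.** Let q be a surgeon's share of CI patients minus that surgeon's share of LPF patients. The surgeon contribution to the variance of the difference is SD² × ICC × Σq². With 102 patients and 10 surgeons, Σq² is about (102/51²) × (1 − 1/10) = 0.0353. At ICC 0.05 this gives 240.25 × 0.05 × 0.0353 = 0.424, an SD of 0.65 MHQ points.

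**4. Adding surgeon to the model.** Allocation was simulated in blocks of 4 or 6 (assumed sizes) within two joint strata, ignoring surgeon. The table gives (a) the SE and power of the unadjusted difference against a random surgeon intercept with the ICC treated as known; (b) simulated power with the surgeon variance estimated by REML; (c) simulated power with fixed surgeon effects. Each pair is without → with the surgeon term. Compare within columns only, since methods and simulation noise differ between them.

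| Assumed ICC | Surgeon-imbalance SD | (a) SE | (a) Power, % | (b) REML power, % | (c) Fixed-effects power, % |
|---|---|---|---|---|---|
| 0 | 0 | no change | no change | 81.1 → 81.1 | 81 → 76 |
| 0.02 | 0.41 | 3.07 → 3.06 | 81.0 → 81.1 | not run | 80 → 77 |
| 0.05 | 0.65 | 3.06 → 3.04 | 81.1 → 81.7 | 79.9 → 80.9 | 81 → 79 |
| 0.10 | 0.92 | 3.05 → 2.98 | 81.3 → 83.1 | 80.4 → 82.2 | 81 → 81 |
| 0.20 | 1.30 | 3.04 → 2.84 | 81.7 → 86.6 | 81.6 → 85.8 | 81 → 85 |

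The random intercept cuts the variance by 0.3%, 1.5%, 4.6% and 13% at ICC 0.02, 0.05, 0.10 and 0.20. With 15 surgeons the gains in (a) are similar: 81.0 → 81.5 at ICC 0.05 and 81.1 → 82.6 at 0.10. With 15 surgeons of unequal size, fixed effects lose more: 80 → 76 at ICC 0.05.

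**5. Validity.** Under no treatment effect, the unadjusted test rejected in 4.6% to 5.5% of simulated trials at ICC 0 to 0.10. With the REML random intercept the rate was 4.4% to 5.5%.

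**6. Joint type.** The documents give no figure for how much of the MHQ variance joint type explains. Because the arms are blocked on it, a share f (after baseline MHQ) shrinks the reported SE by √(1 − f). For assumed f of 0.02, 0.05 and 0.10, the SE of 3.07 becomes 3.04, 2.99 and 2.91.

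**The case against.** The strongest reply is that almost nothing is at stake. The surgeon ICC is unknown, and at 0.05 or below the gain is under one power point in (a) and about one in (b). The imbalance is random error already contained in the unadjusted SE. Section 8.2 also builds in margin by "assuming a correlation value of 0.0 between baseline and 12-month post-randomization MHQ scores": an assumed correlation of 0.3 would cut the variance by 0.3² = 9%, more than the 4.6% from a surgeon term at ICC 0.10. Further, Section 8.3 gives no model at all, so the plan is silent on surgeon rather than opposed to it, and 10 surgeons is a recruitment assumption. All of this stands, and it is why the point is minor. It does not argue against the change: the random intercept cost no detectable power at ICC 0, and joint type is already built into the design. The statistician is to be blinded to group labels (4.5.2), which limits the risk of choosing the model after seeing data, but a written model settles the question.

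A second reply concerns the sources of surgeon variation. LPF technique and CI experience are specific to one treatment, and a common intercept does not model them. This also stands. A reader might infer from the learning-curve remark that the comparison is distorted by inexperience and that a surgeon term would correct it. The documents do not support that: Section 5.4 answers the learning curve with a training video and a minimum of 10 successful procedures, and a surgeon-by-treatment effect was not examined here.

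**Conclusion.** The omission is real and its consequence is small. Joint type and surgeon are both absent from the stated analysis, so some precision is given up if outcomes differ by either. For surgeon, the gain from a random intercept is about 0.1, 0.6, 2 and 5 power points at assumed ICCs of 0.02, 0.05, 0.10 and 0.20. These figures rest on 102 evaluable patients, 10 surgeons of similar size, SD 15.5, the ICC treated as known and a surgeon effect common to both arms. The gain from joint type cannot be sized from the documents.

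Two stronger readings should be set aside. A reader might infer from the one-in-four chance of a 9:4 split that the comparison is biased or the test unsafe. It is neither: at ICC 0.05 the effect on the difference has an SD of 0.65 points, against an SE of about 3.06 and a target of 8.7, and type I error holds. A reader might also size the gain by multiplying the SD by √(1 − ICC). For surgeon that overstates it, because it presumes arms balanced within surgeon, which this randomization does not provide.

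Severity: minor.

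**What to change.** In Section 8.3, state the primary model as 12-month MHQ on treatment, baseline MHQ and primary joint type, with a random intercept for surgeon. Specify random rather than fixed, because fixed surgeon effects lose power below an ICC of about 0.10. Set in advance a rule for pooling very low-volume surgeons within centre. Use the same terms for ROM and the other HRQL outcomes.

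The cost is SAP wording only: surgeon and joint type are known for every patient, and neither the sample size nor the randomization changes. The downside is a slightly more complex model, with negligible gain from the surgeon term if surgeons do not differ.
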